This study uses a blocked randomized controlled design. The study subjects will be selected using a convenience sampling method. When selected, the subjects will be randomly assigned to either one of the 4 study groups using a stratified random strategy (stratifying variable= academic year of study). The study groups (PMR, MM, GI, Control group) will received 5 30-minute weekly sessions of their assigned intervention over 5 weeks. However, there will be a 4-hours workshop explaining the purposes and techniques of the study interventions before introducing the actual session. The subjects will be asked and encouraged to practice their assigned intervention for 30 minutes daily at home. The dependent variables will be measured three times for the 4 groups: at baseline, at the middle (after the second session), and at the end of intervention.

Participants

Participants are undergraduate nursing students who will be selected using a stratified random sampling method from Jordan University of Science and Technology. Jordanian undergraduate nursing students will be asked to participate in the current study if they are at least 18 years old and taking a clinical course. Exclusion criteria include students who are 1) practicing of any type of relaxation techniques, such as yoga, guided imagery, meditation, cognitive behavioral therapy, or 2) taking hypnotics, sedatives, anxiolytic, anti-depressant, anti-inflammatory drugs.

Determination of Sample Size

Using G* Power software 3.1, mixed-design (within groups-between groups) repeated measures ANOVA, an alpha of .05, a power of 0.8, the number of measurements of 3, the number of groups of 4, and a moderate effect size of 0.25, the sample size of 180 was generated. A 15 % attrition rate was reported in a previous study with variables similar to the present study [14]. Considering an expected attrition rate of 15 %, the required final total sample size 210.

Intervention

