Control Group. Participants in the control condition will be instructed to sit with their eyes closed during the intervention periods. Participants in the control group will follow an identical time period as the experimental groups. For instance, when the experimental groups will practice for 30 minutes, the participants in the control group will be asked to sit with eyes closed and relax for 30 minutes.

Procedure

First, approvals from the JUST institutional review boards will be obtained. After that, a translation from English to Arabic and pilot testing of the English versions of the scales used in the current study will be performed. The scales used in the study will be introduced for 30 Jordanian undergraduate nursing students, and then the construct validity, reliability (internal consistency), readability of these scales will be examined.

After taking the permission of the dean of nursing college and class's instructors, the PI will visit students in their classrooms. As the lecture finishes, The PI will announce the

title and objectives of the study and ask the students who would like to participate to contact him using a business card including the PI's contact information (his name, phone number, and email) given for each one. The contact information will be used only for the purpose of the study. The PI will arrange an initial meeting to meet with students who would like to participate on another day in a private room at the university. At this meeting, the PI will inform the students the study's objectives, risks, benefits, and confidentiality and answer questions that they have about the study. Also, they will be assured that they have the full right to refuse or discontinue the participation at any time and that such refusal or discontinuation will not affect their academic achievements in any way. If agree to participate and eligibility criteria are met, informed consent will be obtained at the meeting. After that, the participants will be randomly assigned equally to the study groups using a stratified random assignment method (stratifying variable= academic year of study). Finally, dates and times for sessions will be set up and sent to the participants using their e-mails.

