In the 4-hour education session, the baseline measurements of the study variables will first be obtained. Then the PI will separately provide a power point presentation to participants in each experimental group as explained previously. At the end of the workshop, to avoid experiment contamination, the participants in each experimental group will be asked not to share any information related to the intervention with subjects in other groups.

The actual training will be introduced to subjects in the experimental groups, using an audio CD designed and produced by the PI based on the Smith's (2005) guidelines and protocols. Based on the ABC Relaxation Theory (Smith, 2005), at least two, and preferably five sessions of actual mind-body training should be provided to evoke relaxation and optimize health [15]. In the proposed study, the dependent variables will be measured at the middle and at the end of intervention to see whether further health benefits occur between these two measurements. The sessions will be provided to the study groups in a private, quiet,

comfortable, and spacious room at the university. The dependent variables will be measured three times for the groups: at baseline, after 2nd actual training session, and at the end of intervention (after 5th session), as mentioned previously.

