Statistical analysis will be conducted using SPSS software (version 23). Descriptive statistics will be used to describe the sample. The sample and variables will be described by measures of central tendency and dispersion appropriate to the level of measurement. Initial analyses will be conducted to ensure that the randomization across covariates was successful. The gender, marital status, employment, nationality, and smoking behavior variables will be all tested at baseline using Chi-square to demonstrate that they are not significantly different

between groups. Independent t-tests will be run at baseline measurements of dependent variables to make sure the study groups will be not significantly different on these variables before introducing the study intervention. One-way- ANOVA will be used to test the study hypotheses. Post hoc t-tests will be run to examine if the study groups will be significantly different on the dependent variables at end of the intervention. In case of having confounding effects of some variables, ANCOVA will be used.

Ethical consideration

Physical or psychological harm or risks that might be associated with the measurement activities or intervention employed in the current study will be minimal. One risk that might have resulted from the study was making demands on the subject's time and venipuncture-related pain. Thus, the subjects were provided with compensations (10 Jordanian Dinars) for their times spent in the study and ELMA cream will be used before blood sampling to decrease venipuncture-related pain. Moreover, trained nurses will draw blood from participants, following the Blood Sampling Guideline of the European Federation of Clinical Chemistry and Laboratory Medicine, 2017.

Potential benefits of the measurement activities and intervention to study subjects included increased knowledge and awareness about their health and mind-body modalities. For society, potential benefits included a greater understanding of the effects of mind-body modalities on stress reduction and the potential improvement of the study population's health. In this study, potential benefits are believed to exceed risks.

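### The hypothesis test is unadjusted, and ANCOVA waits on an undefined confounding condition; the outcome's baseline value and academic year should be in the model by default

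*Combined protocol and SAP*

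**What the plan says.** The Statistical Analysis section names the main test: "One-way- ANOVA will be used to test the study hypotheses". Post hoc t-tests follow at end of intervention. Adjustment appears in one sentence: "In case of having confounding effects of some variables, ANCOVA will be used".

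The same section begins with baseline checks: "Initial analyses will be conducted to ensure that the randomization across covariates was successful". Gender, marital status, employment, nationality and smoking are compared by chi-square, and for the outcomes, "Independent t-tests will be run at baseline measurements of dependent variables to make sure the study groups will be not significantly different". This is the only stated use of the outcomes' baseline values.

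Academic year stratifies the allocation. The Design section assigns subjects "using a stratified random strategy (stratifying variable= academic year of study"), and the Procedure section says the same: "the participants will be randomly assigned equally to the study groups using a stratified random assignment method". Academic year appears neither in a model nor in the chi-square list.

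Two other places bear on the adjustment set. The Instruments section says that coping and fear of blood sampling are measured to examine their confounding effects, and the Covariates section calls coping a covariate. The Statistical Analysis section ties neither to a model.

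**The concern.** A covariate belongs in a randomised comparison because it predicts the outcome, not because the groups happen to differ on it. Each outcome is measured at baseline, after session 2 and after session 5, so its own baseline value is the obvious predictor. Academic year was thought important enough to stratify on. When a prognostic stratification factor is left out, the group means are balanced on it but its variance stays in the error term, so the test rejects too seldom.

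The conditional sentence does not say what counts as confounding, which covariates then enter, or when this is decided. Two analysts could both follow the plan and report different p-values for the same outcome. Baseline significance tests do not close the gap. After randomisation, differences arise by chance, so such tests cannot show that allocation worked, and a non-significant result is no reason to omit a predictor.

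**Working it through.** **Inputs from the documents** (Determination of Sample Size): alpha 0.05, power 0.80, 4 groups, f = 0.25, N = 180 before attrition.

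**Assumed, because the documents do not give them:** baseline-to-end correlation r = 0.1, 0.3, 0.5 or 0.7, and the share of outcome variance explained by academic year.

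**1. The plan's own figure.** For one-way ANOVA, the noncentrality is λ = N f² = 180 × 0.0625 = 11.25, with 3 and 176 degrees of freedom. Power is 0.804. The smallest multiple of 4 that reaches 80% is 180, so the stated N is reproduced.

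**2. Adding the baseline value.** λ = N f² / (1 − r²), with 3 and 175 degrees of freedom.

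| r | 1 − r² | λ | Power | Gain over 80.4% (points) |
|---|---|---|---|---|
| 0.1 | 0.99 | 11.36 | 80.8% | 0.4 |
| 0.3 | 0.91 | 12.36 | 84.3% | 3.9 |
| 0.5 | 0.75 | 15.00 | 91.1% | 10.7 |
| 0.7 | 0.51 | 22.06 | 98.3% | 17.9 |

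**3. Adding academic year as well.** With year entered as two terms (three years assumed) and r taken within year, 1 − R² = (1 − R²_year)(1 − r²). If year explains 5% of the variance, power is about 83%, 86%, 92% and 99% at the four values of r. If it explains 10%, power is about 85%, 88%, 94% and 99%.

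**4. Cost if neither covariate predicts.** With R² = 0 and three covariate terms, power is 80.38% against 80.40%, a loss of about 0.02 points.

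**5. Leaving out a prognostic stratification factor.** In a simulation under the null (N = 192, four equal strata, balanced within strata, r = 0.5, 6,000 runs), the unadjusted test's type I error was about 3.4% when year explained 10% of the variance and 2.4% when it explained 20%. The model with year and baseline stayed near 5%.

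**6. Effect of the open choice.** In simulation under the design effect, ANOVA and baseline-adjusted ANCOVA reached opposite significance verdicts for an outcome in about 7%, 13% and 18% of trials at r = 0.3, 0.5 and 0.7. The current text could support either result.

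**7. One possible trigger.** Suppose ANCOVA is used for an outcome only when any of its six baseline pairwise t-tests has p < 0.05. The plan does not state this rule. By simulation it fires for about 20% of outcomes. At the four values of r, power is 80%, 81%, 83% and 84%, and type I error is 5.0%, 4.6%, 3.9% and 2.9%. At r = 0.5 the rule recovers about 3 of the 11 points available.

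**8. Baseline timing.** The Procedure section assigns participants first and measures baseline later: "In the 4-hour education session, the baseline measurements of the study variables will first be obtained". It does not say whether they know their group by then. If that knowledge shifted one arm's baseline by an assumed 0.1 SD but not its end value, the adjusted difference would move by about r × 0.1, that is 0.01 to 0.07 SD.

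**The case against.** The strongest reply is that the planned test is valid. Randomisation makes the unadjusted comparison unbiased, and it has 80% power at the design effect. The gain rests on correlations that the documents do not supply, and at r = 0.1 it is negligible. All of this stands. It limits the point to precision and pre-specification, but it does not defeat it, because the covariates cost almost nothing when they do not help.

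A second reply is that confounding effects are mentioned elsewhere only for coping and fear of blood sampling, so ANCOVA may be meant for those variables. This is fair. The candidates are not wholly unnamed, and the trigger in step 7 is only one reading. But no rule says whether or when those two enter a model, and neither is the baseline value or academic year.

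Stronger readings are tempting but unsupported:

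- **The trial is underpowered or its estimates biased.** Steps 1 and 2 show no shortfall at the design effect, and randomisation protects the estimate.
- **The conditional wording inflates type I error.** Under the trigger in step 7 the procedure is conservative. Sizes of 5.5%, 6.5%, 7.5% and 8.5% at the four values of r would need an analyst who reports whichever model is significant. The plan does not state that practice, though it does not rule it out.
- **The trigger would fire in about 20% of trials.** The 20% is per outcome. On a count of 14 outcomes (9 scale scores, 5 biomarkers), treated as independent, at least one would fire in 1 − 0.8¹⁴, about 96% of trials.

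Finally, adjustment carries the small exposure in step 8, which the unadjusted end-value comparison would not have. This is a reason to fix the timing of baseline or report it.

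**Conclusion.** The point holds as a recommendation on precision and pre-specification, not as a flaw in validity. No stated model contains the outcome's baseline value or the stratification factor, and the condition for ANCOVA is undefined.

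At N = 180 and f = 0.25, the precision forgone by omitting baseline ranges from almost nothing at r = 0.1 to about 18 points of power at r = 0.7. Academic year adds to this only if it predicts the outcome, and in that case the unadjusted test is also conservative. The open choice of model matters whatever the correlation. The correlations and the year effect are assumptions; the absence of a rule is plain in the text.

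Two neighbouring matters are separate and are not settled here: the sample size is attributed to a "mixed-design (within groups-between groups) repeated measures ANOVA" while the analysis is one-way, and the number of t-tests.

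**What to change.** Replace the conditional ANCOVA sentence with:

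> For each outcome, the end-of-intervention comparison uses ANCOVA with group, that outcome's baseline value and academic year, regardless of observed balance; post hoc comparisons are taken from the same model.

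In addition:

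- Label any analysis of the measurement after session 2 as secondary.
- Present baseline characteristics descriptively, and do not use chi-square or t-tests to decide on adjustment.
- If coping and fear of blood sampling are adjusted for, do so in a named sensitivity analysis using baseline values only.
- Take baseline before participants learn their group, or state the timing as a limitation.

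The cost is mainly wording. Baseline values and academic year are already collected, and the sample size does not change. The timing of baseline needs a small procedural change or one sentence.
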